### 6.2.2 Nivolumab administration days

- Physical exam, vital signs, ECOG Performance Status, Toxicity
- Hematology: CBC with diff includes total WBC, hemoglobin, hematocrit, platelet count and differential of the WBC including absolute counts
- Serum chemistries: Comprehensive metabolic profile (COMP) includes sodium, potassium, chloride, bicarbonate, BUN, creatinine, AST, ALT, alkaline phosphatase, total bilirubin.

- Magnesium, phosphorus, LDH
- Every 12 weeks until discontinuation/completion of nivolumab on trial: TSH, free T3, free T4 (Only If Clinically Indicated: FSH, LH, ACTH).
- Whole blood will be collected for correlative analysis at certain time points. See Section 6.4 Time and Events Table including footnote #8 for the time points and the Lab Manual for collection, labeling and shipping instructions
- Blood draw for ADA (anti-drug antibody) analysis will be collected at the time points listed in Section 6.4 Time and Events Table.
- Prior to dose # 1 (subsequently ONLY if clinically indicated): 12-lead Electrocardiography
- At week 12: Echocardiogram
- Nivolumab administration will be over 60 minutes ( $\pm$  10 minutes) at a dose of 480 mg intravenously. Pre-medications or rescue medications are not specified by protocol and will be per institutional guidelines/treating investigator.
- Continue Nivolumab every 4 weeks until i) progression noted or ii) up to 48 weeks completed from start of protocol therapy (week 1) - refer to sections 5.4, 5.5. and 5.7. Nivolumab may be continued by treating investigator beyond this period off-study at his or her discretion and clinical judgment.
- Clinic visits: For patients who continue on nivolumab on trial nivolumab: every 4 weeks (from week1) with scans as in Section 6.4 Time and Events Table below.
- At week 12 and then every 12 weeks: Computed tomography of the chest, computed tomography or magnetic resonance imaging of the abdomen and pelvis, and only if clinically indicated: computed tomography or magnetic resonance imaging of the brain

#### **6.2.3 In between clinic visits**

- Study nurse or coordinator will call patient at least once a week in the first 12 weeks between clinic visits to evaluate for toxicity.

#### **6.2.4 End of Treatment Visit after protocol specified therapy (IL2 and nivolumab) termination**

- Physical exam, vital signs, ECOG Performance Status, Toxicity
- Hematology: CBC with diff includes total WBC, hemoglobin, hematocrit, platelet count and differential of the WBC including absolute counts
- Serum chemistries: Comprehensive metabolic profile (COMP) includes sodium, potassium, chloride, bicarbonate, BUN, creatinine, AST, ALT, alkaline phosphatase, total bilirubin

- Magnesium, phosphorus, LDH
- TSH, free T3, free T4 (Only If Clinically Indicated: FSH, LH, ACTH)

**6.3 Follow-Up Procedures**

For patients who have stopped all protocol specified therapy (IL2 and nivolumab for up to 48 weeks), follow up will be done every 12 weeks (counting from week 1) via phone or other forms of communication. In these patients, scans and/or labs will be per the treating investigator’s discretion/per standard of care and not dictated by the protocol.

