- 3: Comprehensive metabolic profile includes sodium, potassium, chloride, bicarbonate, BUN, creatinine, AST, ALT, alkaline phosphatase, total bilirubin. TSH, free T3, free T4 at baseline and then repeated every 12 weeks. (IF Clinically Indicated ONLY: FSH, LH, ACTH)
- 4: With or without intravenous contrast, before or on associated visit.
- 5: Only if clinically indicated
6. Continue Nivolumab on trial every 4 weeks until i) progression noted and no clinical benefit as determined by treating investigator or ii) up to 48 weeks completed from start of protocol therapy (week 1). Please note that nivolumab could be continued by the treating investigator off-trial beyond the 48-week duration at his or her clinical discretion.
7. An archived tissue block must be **identified** with intent to submit for analysis prior to registration. See the Lab Manual for collection, labeling and shipping instructions.
- 8: Whole blood is to be collected at 5 time points: pre-all study therapy, post first HD IL2 cycle but pre-nivolumab, after the first dose of nivolumab but before the second dose of nivolumab, post second HD-IL2 cycle (before the next dose of nivolumab) and at 12 weeks on days indicated prior to study drug being administered on that day. In some patients, due to the exact timing of dose #1 of nivolumab in that patient, two of these time points might coincide and in those patients, only 4 time points will be drawn. Serum will be collected at baseline only. See the Lab Manual for collection, labeling and shipping instructions.
- 9: For patients who have stopped all protocol specified therapy, follow up will be done every 12 weeks  $\pm$  4 weeks x total of 24 months (counting from week 1) via phone or other form of communication. In those patients, scans and/or labs will be per the treating investigator's discretion/standard of care and will not be dictated by protocol.
10. WOCBP: urine or serum pregnancy test for women of child bearing potential, see section 6.1.12
11. For as long as subjects continue on nivolumab (i.e. up to 48 weeks on treatment, or beyond the 48 week duration of treatment per treating investigator's discretion): Survival status assessment at least every 12 weeks  $\pm$  4 weeks x total of 24 months (counting from week 1) with scans as noted.

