##### **7.1.4.3 Evaluation of Best Overall Response**

The best overall response is the best response recorded from the start of the treatment until disease progression/recurrence (taking as reference for progressive disease the smallest measurements recorded since the

treatment started). The patient's best response assignment will depend on the achievement of both measurement and confirmation criteria.

Target Lesions	Non-Target Lesions	New Lesions	Overall Response	Best Response for this Category Also Requires:
CR	CR	No	CR	≥4 wks. confirmation
CR	Non-CR/SD	No	PR	≥4 wks. confirmation
PR	Non-PD	No	PR	
SD	Non-PD	No	SD	documented at least once ≥4 wks. from baseline
PD	Any	Yes or No	PD	no prior SD, PR or CR
Any	PD*	Yes or No	PD	
Any	Any	Yes	PD	

* In exceptional circumstances, unequivocal progression in non-target lesions may be accepted as disease progression.
 
Note: Patients with a global deterioration of health status requiring discontinuation of treatment without objective evidence of disease progression at that time should be reported as “symptomatic deterioration”. Every effort should be made to document the objective progression even after discontinuation of treatment.
				

Note: If subjects respond to treatment and are able to have their disease resected, the patient's response will be assessed prior to the surgery.

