**7.1.6 Progression-Free Survival**

Progression-free survival (PFS) is defined as the duration of time from start of treatment to time of progression.

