## 11.2 Data Analyses Plans

Primary Endpoint Analysis:

Phase 1b: DLT count and proportion will be reported. Type, grade and attribution will be described by body system in the first 10 DLT evaluable patients. Number of IL-2 cycles and doses and Nivolumab doses will be summarized.

Phase II: Overall response rate at 12 weeks will be reported with the sample size and proportion of evaluable patients and the corresponding 95% exact binomial confidence interval.

Secondary Endpoint Analyses:

Safety will be defined by frequency of drug-related grade 3-5 adverse events including adverse events of interest within the duration of protocol, specified therapy and an additional 60 days following the last dose with the combination of HD IL2 and nivolumab, as assessed by NCI's CTCAE version 4.0. Counts and frequencies will be reported by body system, type and grade. Cycles and of each drug and doses/cycle of IL-2 will be described using descriptive statistics.

Survival endpoints are 24-month Overall Survival (OS) and 24-month Progression-Free Survival (PFS) as assessed by RECIST 1.1 criteria in subjects treated with the combination. Product-limit estimates from Kaplan-Meier methods will be used to report the 24-month OS and PFS proportions with 95% confidence intervals. Kaplan-Meier figures will be produced.

Interim Analysis for efficacy: An interim analysis for efficacy is planned after 12 response evaluable patients have been enrolled (total in the phase I b/II portions). If 2 or less patients have a response at 12 weeks then the trial will terminate. .

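### For patients off nivolumab without progression, 24-month PFS rests on discretionary scans, with no censoring rule and two conflicting scan rules after week 48

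*Combined protocol and SAP*

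**What the plan says.** **Endpoint.** Study Endpoints and Section 11.2 list "24-month Progression-Free Survival (PFS) as assessed by RECIST 1.1 criteria in subjects treated with the combination" as a secondary endpoint. On the estimator, Section 11.2 says "Product-limit estimates from Kaplan-Meier methods will be used to report the 24-month OS and PFS proportions with 95% confidence intervals". Section 7.1.6 defines PFS as the "duration of time from start of treatment to time of progression". Neither section gives a rule for censoring, for missed scans or for death without recorded progression.

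**Scans on treatment.** Section 6.2.2 schedules imaging as follows: "At week 12 and then every 12 weeks: Computed tomography of the chest", with abdomen and pelvis alongside. Protocol nivolumab runs to 48 weeks from week 1 at most (Sections 5.5 and 6.2.2).

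**Scans after treatment.** Section 6.3 covers patients who have stopped all protocol therapy. Contact is every 12 weeks by telephone or similar, and scans are at the investigator's "discretion/per standard of care and not dictated by the protocol". Footnote 9 of the Time and Events Table (Section 6.4) repeats this: "discretion/standard of care and will not be dictated by protocol". The imaging and tumor-measurement cells in the Follow-Up column carry that footnote. The end-of-treatment visit (Sections 6.2.4 and 6.4) has no imaging.

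**A second rule.** Footnote 11 covers patients for as long as they stay on nivolumab, including past week 48. It gives them survival status at least every 12 weeks to 24 months from week 1, together with the scheduled scans.

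**The concern.** A RECIST progression date needs a scan; a telephone call cannot supply one. Patients who leave therapy without progression, whether by completing 48 weeks, through toxicity or by choice, largely determine the 24-month value, because those who progressed on treatment already have their event. For this group the protocol stops scheduling the measurement on which the endpoint depends.

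Two gaps make this worse. Section 11.2 does not say whether a patient last scanned at week 48 and telephoned at month 24 is event-free at month 24 or censored at week 48, and those readings can give very different curves. In addition, footnote 11 on one side and Section 6.3 with footnote 9 on the other both apply to a patient who has finished protocol therapy but continues nivolumab off study. If footnote 11 governs, scan intensity depends on a treatment decision that may be related to prognosis.

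At stake is whether the reported 24-month PFS and its interval can be interpreted.

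**Working it through.** **1. The plan's own figures.** The documents give no expected PFS, sample size or power for PFS. The only design figures concern 12-week response: stop if at most 2 of 12 respond, positive if more than 8 of 23 respond. Exact binomial calculation gives an early-stop probability of 0.391 at a 25% response rate and 0.036 at 46%, power of 0.801 and type I error of 0.094. These agree with the stated 39%, 3.6%, 80% and 10% (the last as a cap). They do not involve PFS.

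**2. Share of the horizon without protocol scans, for a progression-free patient off nivolumab.** Formula: (104 − week of last protocol scan) / 104.

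| Last protocol scan | Calculation | Share |
|---|---|---|
| Week 48 | 56/104 | 54% |
| Week 36 | 68/104 | 65% |
| Week 24 | 80/104 | 77% |
| Week 12 | 92/104 | 88% |

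A patient on nivolumab to month 24 under footnote 11 has scheduled scans throughout, so the gap is zero. Early stopping is foreseeable. Section 11.1 lets the trial proceed with up to 5 of 10 patients having grade 3 or 4 immune-mediated events, and several tables in Section 5.2.1 discontinue nivolumab for such events.

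**3. Possible size of the effect.** Assume exponential PFS, S(t) = 2^(−t/m), with the median m in weeks = months × 52.18/12. The 4.6-month median is the nivolumab monotherapy figure in Section 1.2; 9 and 12 months are assumptions. What the curve shows at week 104 is:

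- True value: S(104).
- 12-weekly scans throughout (last scan before week 104 is week 96): S(96).
- Detection after week 48 late by d weeks: S(104 − d), that is S(92) for 12 weeks and S(80) for 24 weeks.
- Nothing detected after week 48 and nobody censored: S(48).

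Example for 9 months: m = 39.1 weeks, so S(96) = 2^(−2.45) = 0.183 and S(80) = 2^(−2.04) = 0.242.

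| Median (months) | True | 12-weekly scans | 12 weeks late | 24 weeks late | Never detected, never censored |
|---|---|---|---|---|---|
| 4.6 | 2.7% | 3.6% | 4.1% | 6.3% | 19% |
| 9 | 15.8% | 18.3% | 19.6% | 24.2% | 43% |
| 12 | 25.1% | 27.9% | 29.5% | 34.6% | 53% |

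Against 12-weekly scanning, a 24-week delay adds 6.3 − 3.6 = 2.7, 24.2 − 18.3 = 5.9 and 34.6 − 27.9 = 6.7 points. A 12-week delay adds 0.5, 1.3 and 1.6 points.

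**4. How many patients could be exposed.** 23 × S(48) gives 4.4, 9.8 and 12.2 patients progression-free at week 48. This is a ceiling for that time point, since it includes anyone scanned under footnote 11 or regularly under standard care. Patients who stop earlier without progression are exposed before week 48 as well.

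**5. Direction.** If unscanned patients count as event-free to their last contact, late detection raises the estimate. If they are censored at the last scan and scans are ordered mainly when progression is suspected, those who progress contribute events while those who stay well leave the risk set early. The estimate can then fall. Section 11.2 does not say which applies.

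**The case against.** The strongest reply is that the gap is narrower than it looks.

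- **Not every patient loses scheduled scans at week 48.** A reader might infer that all protocol imaging ends by then. Footnote 11 says otherwise for patients continuing nivolumab, and patients still progression-free at week 48 are those in whom continuation would arise. This stands. What remains is the conflict between the two rules and the exposure of patients who are off nivolumab.
- **Some capture is provided for.** Section 7.1.4.3 addresses "Patients with a global deterioration of health status requiring discontinuation of treatment without objective evidence of disease progression at that time" and asks sites to try to document objective progression even after treatment ends. Section 15.0 foresees long-term data from chart review or patient contact. This stands in part. The first covers symptomatic deterioration, not completion, toxicity or choice; the second does not require scan dates or RECIST results.
- **Standard-of-care scans may be as frequent as every 12 weeks.** The documents neither establish nor exclude this. If so, the distortion is small.
- **The effect is modest beside sampling error.** At a 24-month PFS of 20% with 23 patients, the approximate 95% half-width is 1.96 × √(0.2 × 0.8/23) = 16 points, against 3 to 7 points for a 24-week delay. This is true, but the interval does not reflect delayed detection or informative censoring.
- **PFS is secondary, with no test or decision attached.** This stands and limits the consequence.

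**Conclusion.** The concern holds for patients off nivolumab without progression. Followed as written, the plan cannot reliably deliver a RECIST-based 24-month PFS for them: 54% of the horizon has no protocol scan for a week-48 stopper, more for earlier stoppers, and no censoring rule settles how the gap is handled. The two post-treatment scan rules also conflict for patients continuing nivolumab after week 48.

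An upward shift of the 24-month figure is likely but not proven. With a 24-week delay it is about 3 to 7 points above 12-weekly scanning. That assumes exponential PFS, medians of 4.6 to 12 months, the same delay for every later progression and no scheduled scans for anyone after week 48.

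Two stronger readings are not supported. The values of 19%, 43% and 53% are a ceiling that assumes no later progression is ever found and nobody is censored; they are not an expected result. Nor is the whole cohort affected: progressions on treatment are sought on schedule. The 12-week response rate and the 23-patient design are untouched.

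**What to change.** 1. In Study Endpoints and Section 11.2, make PFS at week 48, the end of the scheduled-scan period, the main PFS landmark. Keep 24-month PFS and label it descriptive.
2. In Section 6.3, have sites record the date and RECIST result of any standard-of-care scan at each existing 12-weekly contact to month 24, for patients without progression. No new scan is required.
3. In Section 11.2, censor PFS at the last adequate tumor assessment, not at the last telephone contact.
4. Report how many at-risk patients had a scan in the 12 weeks before each landmark.
5. Reconcile Section 6.3 and footnote 9 with footnote 11, so that one rule applies to patients continuing nivolumab after week 48.

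The cost is wording in three sections, one extra CRF page and a shorter main PFS landmark. Some weakness remains. Patients who stop early are still under-imaged before week 48, and censoring at the last scan can be informative when scans follow symptoms. The scan-completeness count will show how far either matters.

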**6.4 Time and Events Table**

	Screen (<28d)	Week 1 IL2 Cycle #1	Nivolum ab Dose #1 	Week 3 IL2 Cycle #2	Nivolum ab Dose #2... 	Week 12	Subsequent 	End of treatment visit 	Follow-Up 
Informed Consent	X								
History, PE, Con Meds, Weight, Vital Signs 	X	X	X	X	X	X	X	X	X
ECOG Performance Status	X	X	X	X	X	X	X	X	
Toxicity Evaluation		X	X	X	X	X	X	X	
HD IL2 eligibility assessment	X								
Pregnancy Test for WOCBP 	X								
CBC with diff and plt 	X	X	X	X	X	X	X	X	
COMP 	X	X	X	X	X	X	X	X	
Mag, Phos, LDH	X	X	X	X	X	X	X	X	
PT/INR	X								
Urine Protein/Creatinine Ratio	X								
Urine output measurement, pulse oximetry measurement.		X (qday)		X (qday)					

	Screen (<28d)	Week 1 IL2 Cycle #1	Nivolumab Dose #1 	Week 3 IL2 Cycle #2	Nivolumab Dose #2... 	Week 12	Subsequent 	End of treatment visit 	Follow-Up 
TSH, free T3, free T4 (IF Clinically Indicated: FSH, LH, ACTH) 	X						X (q 12 weeks)	X	
Total Creatinine Kinase, Troponin T		X (day 5)		X (day 19)					
12-lead ECG	X		X				X (IF clinically indicated)		
CT chest 	X					X	X (q 12 weeks)		X 
CT or MRI abdomen/pelvis 	X					X	X (q 12 weeks)		X 
CT or MRI brain 	X					X	X 		X 
Tumor Measurements	X					X	X (q 12 weeks)		X 
Central line placement		X (day 1)		X (day 15)					
HD-Interleukin-2		X (D1-5)		X (D15-19)					
Nivolumab 			X		X	X	X... 		
Archived Tumor Tissue 	X								
Blood draw for Anti-Drug Antibody Analysis 	X		X		X	X	X (q12 weeks)		
Whole blood, 	X		X	X	X	X			
Serum 	X								
Echocardiogram 	X					X			
Study RN/Coordinator Call 		X	X	X	X	X			

**All assessments have a window of ± 3 business days except for imaging/tumor measurements where a window of ± 7 business days will apply.**

- 1: Vital signs will include temperature, pulse, respirations, blood pressure); height will be obtained at screening only.
- 2: CBC with diff includes total WBC, hemoglobin, hematocrit and differential of the WBC including absolute counts.
- 3: Comprehensive metabolic profile includes sodium, potassium, chloride, bicarbonate, BUN, creatinine, AST, ALT, alkaline phosphatase, total bilirubin. TSH, free T3, free T4 at baseline and then repeated every 12 weeks. (IF Clinically Indicated ONLY: FSH, LH, ACTH)
- 4: With or without intravenous contrast, before or on associated visit.
- 5: Only if clinically indicated
6. Continue Nivolumab on trial every 4 weeks until i) progression noted and no clinical benefit as determined by treating investigator or ii) up to 48 weeks completed from start of protocol therapy (week 1). Please note that nivolumab could be continued by the treating investigator off-trial beyond the 48-week duration at his or her clinical discretion.
7. An archived tissue block must be **identified** with intent to submit for analysis prior to registration. See the Lab Manual for collection, labeling and shipping instructions.
- 8: Whole blood is to be collected at 5 time points: pre-all study therapy, post first HD IL2 cycle but pre-nivolumab, after the first dose of nivolumab but before the second dose of nivolumab, post second HD-IL2 cycle (before the next dose of nivolumab) and at 12 weeks on days indicated prior to study drug being administered on that day. In some patients, due to the exact timing of dose #1 of nivolumab in that patient, two of these time points might coincide and in those patients, only 4 time points will be drawn. Serum will be collected at baseline only. See the Lab Manual for collection, labeling and shipping instructions.
- 9: For patients who have stopped all protocol specified therapy, follow up will be done every 12 weeks  $\pm$  4 weeks x total of 24 months (counting from week 1) via phone or other form of communication. In those patients, scans and/or labs will be per the treating investigator's discretion/standard of care and will not be dictated by protocol.
10. WOCBP: urine or serum pregnancy test for women of child bearing potential, see section 6.1.12
11. For as long as subjects continue on nivolumab (i.e. up to 48 weeks on treatment, or beyond the 48 week duration of treatment per treating investigator's discretion): Survival status assessment at least every 12 weeks  $\pm$  4 weeks x total of 24 months (counting from week 1) with scans as noted.
12. Nivolumab should optimally be started on week 2 (after the first 3 subjects, please see statistical section 11) but can be started up to 3 weeks after first dose of IL-2 but NOT be on the same week as any HD IL2 cycle.
13. At baseline, a dobutamine stress echocardiogram or equivalent will be performed. Standard 2-D transthoracic or surface echo cardiogram will be performed.
14. A call from the study nurse or coordinator will occur in between clinic/hospital visits once weekly for the first 12 weeks.
15. Blood draw for Anti-Drug Antibody Analysis to be collected: pre-all study therapy, prior to Nivolumab dose 1, prior to Nivolumab dose 2, at week 12 (prior to Nivolumab dose), and every 12th subsequent week (prior to Nivolumab dose) until the end of protocol treatment.
16. Within 60 days after protocol specified therapy (IL2 and nivolumab) termination.

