
Study Duration	
24 months of accrual
 
24 months of follow-up (counting from week 1)

Study Center(s)	
4 Sites including lead site: University of Michigan.

Objectives	
Phase Ib:
 
Primary Objective:
 
 
1. To estimate the safety and toxicities of High Dose Interleukin-2 in combination with the immune checkpoint inhibitor Nivolumab in metastatic clear cell renal cell carcinoma.
 
 
Phase II:
 
Primary Objective:
 
 
1. To estimate the efficacy of High Dose Interleukin-2 in combination with the immune checkpoint inhibitor Nivolumab in metastatic clear cell renal cell carcinoma.
 
 
Secondary Objectives:
 
 
1. To determine the safety of High Dose Interleukin-2 in combination with Nivolumab in metastatic clear cell renal cell carcinoma.
 
2. To profile circulating T cell repertoire by flow cytometry before and during therapy.
 
 
Exploratory Objectives:
 
 
1. To bank tissue and serum specimens for correlative analyses and anti-drug antibody testing in the future.
 

Number of Subjects	
Number of evaluable subjects (those who receive at least 1 dose of HD IL2 and at least 1 dose of nivolumab) = 23. Subjects in the Phase 1b portion will be included in the overall toxicity and efficacy analysis of the study. Subjects who are not evaluable will be replaced. Up to 28 patients may need to be registered (enrolled) in order to obtain the 23 evaluable patients.

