**5.7 Duration of Follow-Up**

Patients will be followed for 2 years (counting from week 1) after completion of/removal from treatment or until death, whichever occurs first. Patients removed from treatment for unacceptable adverse events will be followed until resolution or stabilization of the adverse events.

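### Follow-up closes at the 24-month OS and PFS landmark with no margin and no required status check at or after month 24

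*Combined protocol and SAP*

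**What the plan says.** **Endpoint.** Section 11.2 states: "Product-limit estimates from Kaplan-Meier methods will be used to report the 24-month OS and PFS proportions with 95% confidence intervals". The Study Endpoints part of section 2.0 lists both among the secondary endpoints.

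**Contacts after therapy.** Section 6.3 says that "follow up will be done every 12 weeks (counting from week 1) via phone or other forms of communication". Footnote 9 in 6.4 adds the tolerance and caps the series, with contacts every 12 weeks plus or minus 4 "weeks x total of 24 months (counting from week 1) via phone or other form of communication". Both leave scans in these patients to the treating investigator or standard of care.

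**Contacts on nivolumab.** Footnote 11 in 6.4 asks for "Survival status assessment at least every 12 weeks", with the same tolerance and the same 24-month cap from week 1.

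**Length of follow-up.** The synopsis gives 24 months from week 1. Section 5.7 says: "Patients will be followed for 2 years (counting from week 1) after completion of/removal from treatment or until death, whichever occurs first". This names two starting points for the same two years.

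**Other route.** Section 15.0 says that long-term data are gathered from time to time by chart review or patient contact, without dates.

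**Not stated.** No section names a last contact, requires a status check at or after month 24, or gives a censoring rule for OS or PFS. Section 7.1.6 defines PFS only by its start and its event.

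**The concern.** A Kaplan-Meier estimate at 24 months needs patients whose status is known at 24 months. Here the follow-up period and the landmark have the same length and, on the synopsis and footnote reading, the same origin. The 12-week contact grid does not land on that day. A site that follows the schedule exactly can make its last call about two months early and regard follow-up as done.

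If survivors are then censored at that call, the curve may have few or no patients at risk at 24 months. The figure labelled as 24-month OS would be an earlier value carried forward, with a confidence interval that belongs to the earlier time. PFS has the same difficulty, and also has no protocol-scheduled imaging once therapy stops.

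**Working it through.** The 24-month length is a design choice, so there is no calculated figure in the plan to reproduce. The check is calendar arithmetic followed by an illustration of size. Weeks are elapsed weeks from week 1 day 1.

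**Inputs.** Interval 12 weeks (6.3); tolerance 4 weeks and total 24 months from week 1 (6.4, footnotes 9 and 11); imaging tolerance 7 business days (6.2, 6.4); 23 evaluable patients (11.1); median OS 25 months for nivolumab and 42.8 months for HD IL-2, and median PFS 4.6 months for nivolumab (1.2).

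**Step 1: the landmark in weeks.** One month = 365.25/12 = 30.44 days. So 24 months = 730.5 days, and 730.5/7 = 104.4 weeks.

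**Step 2: contacts near the landmark.**

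| Nominal contact | Months | Window, weeks | Window, months |
|---|---|---|---|
| Week 96 | 22.08 | 92 to 100 | 21.16 to 23.00 |
| Week 108 | 24.84 | 104 to 112 | 23.92 to 25.76 |

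Week 96 is the last nominal contact inside 104.4 weeks and falls 104.36 − 96 = 8.36 weeks short. The week-108 window overlaps the 24-month period only from week 104 to week 104.36: 0.36 × 7 = about 2.5 days.

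**Step 3: scans.** Seven business days is roughly 1.5 weeks. Where the 12-weekly scan grid still applies (patients continuing nivolumab, footnote 11), a week-96 scan falls by about week 98 and a week-108 scan not before about week 106. Neither window contains week 104.4. For patients off therapy the protocol schedules no scan.

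**Step 4: size.** Assume exponential survival, S(t) = exp(−ln 2 × t / median). Assume also that survivors are censored at last contact and that deaths after it are not captured, so the earlier value is carried forward.

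| Endpoint, median | True value at 24 months | Week 96 | Weeks 100 to 92 | Overstatement |
|---|---|---|---|---|
| OS, 25 months | 51.4% | 54.2% | 52.9% to 55.6% | 1.5 to 4.2 points |
| OS, 42.8 months | 67.8% | 69.9% | 68.9% to 71.0% | 1.1 to 3.2 points |
| PFS, 4.6 months | 2.7% | 3.6% | not computed | 0.9 points at week 96 |

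Worked line: exp(−0.6931 × 24/25) = 0.514 and exp(−0.6931 × 22.08/25) = 0.542.

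**Step 5: scale against sampling error.** With 23 patients, a proportion near 50% and no censoring, the half-width of a 95% interval is 1.96 × √(0.5 × 0.5/23) = 0.204, about 20 points. At 51.4%, about 0.514 × 23 = 12 patients would be alive at 24 months. The schedule does not ensure that any of them is documented at risk then.

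**The case against.** A reader might infer that week 96 is the final contact, that every survivor is therefore censored before 24 months, and that 24-month OS is undefined. The documents do not support that, for these reasons:

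- No section names week 96 as the last contact. Footnote 9 fixes a duration, and a closing call at month 24 is compatible with it. If the 4-week tolerance applies to each gap, eight contacts about 13.04 weeks apart end at week 104.4.
- The week-108 contact may be made from week 104, so its window opens inside the period and covers the landmark.
- Footnote 11 sets a minimum frequency, so extra checks are allowed for patients on nivolumab.
- Section 15.0 allows chart review, which could supply a date last known alive beyond month 24.
- If the two years in 5.7 run from the end of treatment, follow-up passes the landmark: to about week 152 (35.0 months) for a patient who stops at week 48.
- Going off study under 5.8.9 requires completing follow-up, and a patient at week 96 has not completed 24 months.
- Censoring at last contact is an assumption.

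All of this stands against the absolute reading. None of it is a requirement. The overlap with the week-108 window is about 2.5 days, and a contact then would normally still precede the landmark. Footnote 11 covers only patients continuing nivolumab. Section 15.0 gives no date. The longer reading of 5.7 conflicts with the synopsis and both footnotes. These provisions permit a check at month 24; they do not secure one.

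It is also fair to say that the numerical effect is small and that the go/no-go rule, based on 12-week response, is untouched.

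**Conclusion.** The point holds in a limited form. Counted from week 1, follow-up ends at the landmark with no margin, and nothing requires vital or progression status at or after month 24. A plan followed as written can leave many survivors last documented at about 21 to 23 months, so the reported 24-month OS could describe an earlier time.

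The likely overstatement is about 1 to 4 points for OS. This rests on exponential survival, on the medians that the protocol quotes for single-agent therapy, on censoring at last contact, and on later deaths going unrecorded. It is minor beside an interval of about ±20 points, and it affects secondary, descriptive endpoints only.

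For PFS the larger gap is the imaging. Once therapy stops, no scan is scheduled, so progression status at 24 months can be missing even when a call is made on time.

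The case for acting is that the remedy is cheap and makes 24-month OS estimable.

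**What to change.** 1. In 6.3 and in footnotes 9 and 11 of 6.4, require one closing vital-status contact or chart review on or after 24 months from week 1 day 1, never earlier (for example, 105 to 109 elapsed weeks). Record the date last known alive, the known progression status and the date of the last scan.
2. In 5.7, reconcile the two starting points for the two years with the synopsis and with footnotes 9 and 11.
3. In 11.2, state that OS is censored at the date last known alive and PFS at the last tumor assessment.
4. Report 24-month PFS with the number still at risk, or report PFS at the latest time that the scans support. The closing contact does not repair PFS.

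The cost is one call or chart review per surviving patient, plus wording changes in four sections. No change to sample size, treatment or the response analysis is needed.
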